## 6.8 Visit 8 Phone Call Follow Up (24 months Post-Operative +/-28 days):

- 1. Recurrence Information (ask participant if they have been evaluated and or treated for recurrence)
- 2. Adverse events evaluation (graft failure, dehiscence, enterocutaneous fistulas, seromas, wound infection, systemic infections, bleeding, etc.)
- 3. Return to OR for additional repair or graft removal (scheduled or date of return)
- 4. Review Medications (After surgery only medications that could impact healing will be recorded including but not limited to steroids, antibiotics)
- 5. Use of Wound V.A.C.® and reason for use.
- 6. Patient Satisfaction form (SF-36)\*
- 7. VAS\*
- 8. Patient contentment with the cosmetic results\*

\*The subjective questionnaires entitled Visual Analog Scale (VAS), SF-36, and Patient Contentment cannot be completed visually by the subject. Therefore, for the VAS, patients will be asked to rate their pain on a scale of 1-10. Patients will be asked questions on the SF-36 and Patient Contentment and the answers will be transcribed by designated study staff.

## 6.9 Unplanned Visit

The procedures performed at an unplanned visit will depend on the nature of the visit. The procedures suggested include:

- 1. Physical assessment to include BMI, general health, etc. (if indicated)
- 2. Physical examination of surgical site (if indicated)
- 3. Lateral and frontal photographs performed with subject sitting and standing (when physically capable). For subjects who are not able to position themselves in a specific manner for the

- 4. photograph due to physical limitations, the reason for this will be recorded in the subject's study record and this will not be considered a protocol deviation.
- 5. Radiographic evidence of recurrence only if clinically indicated
- 6. Newly diagnosed medical issues
- 7. Medication updates, if any
- 8. Adverse events since last visit (i.e. graft failure, enterocutaneous fistula, seromas, wound infection, systemic infection, bleeding, etc.)
- 9. Physical evaluation for hernia recurrence
  - \*\*\*Once a subject has been diagnosed with a true hernia recurrence (either by physical exam or by CT Scan), he/she will be followed only for the planned re-operation (if indicated) and details of the etiology of the recurrence will be captured in the subject's study binder (CRF), when available. The subject's will only be followed to capture information about the reoperation once a recurrence is diagnosed.
  - \*\*\*There is no need to capture implant related data or to conduct follow up visits between the diagnosis of recurrence and the operation for the recurrence. If a participant is not scheduled for a re-operation, his/her study participation will end at this point and this information will be documented on the CRF.
- 10. Clinical evidence of eventration, implant failure, implant related complications, etc. Photographs of the surgical site may be taken to document evidence of adverse events, eventration, implant failure, implant related complications, etc.
- 11. Return for repair since last visit.
- 12. Patient Satisfaction form (SF-36)\*
- 13. VAS\*
- 14. Patient contentment with cosmetic results\*

\*IF the subjective questionnaires entitled Visual Analog Scale (VAS), SF-36, and Patient Contentment cannot be completed visually by the subject for the VAS, patients will be asked to rate their pain on a scale of 1-10. Patients will be asked questions on the SF-36 and Patient Contentment and the answers will be transcribed by designated study staff.

#### **6.10 Schedule of Events:**

## **Schedule of Events**

	Visit 1 Baseline	Visit 2 Surgery	Visit 3 Hospital Discharge (-2 days)	Visit 4 6 Weeks (+/- 1 week)	Visit 5 3 Months (+/- 14 days)	Visit 6 6 Months (+/- 28 days)	Visit 7 12 Months (+/- 28 days)	Visit 8 Telephone 24 Months (+/- 28 days)
Informed Consent	X							
Physical Exam	Х		Х	Х	Х	Х	Х	
Medical, Social, Surgical History	Х	Х						
Medications	X	X	X	X	X	Х	X	X
Adverse Events		X	Χ	X	X	X	X	X
SF36*	X				X	X	X	X
VAS*	X				X	X	X	X
Clinical Evaluation	X		Х	X	X	X	X	
Photographs	Х	Х	Х	Х	Х	Х	х	
Patient Contentment with cosmetic results*							х	х

\*If withdrawn early complete patient contentment cosmetic results.

\*If the subjective questionnaires entitled Visual Analog Scale (VAS), SF-36, and Patient Contentment cannot be completed visually by the subject, for the VAS, patients will be asked to rate their pain on a scale of 1-10. Patients will be asked questions on the SF-36 and Patient Contentment and the answers will be transcribed by designated study staff.

## VII. Safety Assessments

## 7.1 Safety Evaluations

For the purpose of this post-marketing trial, only adverse events or serious adverse events that are related to the surgical procedure or device will be recorded. Safety will be assessed by recording the nature, intensity and duration of all device related adverse events (AEs) and their relationship to the device.

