# 2.4.3 Safety Endpoints

- Type of Adverse Events (volunteered and elicited).
- Frequency of Adverse Events (volunteered and elicited).

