#### 5.3.2 Randomization

Patients who are consented and enrolled in the study will be randomized to receive either one of the two hernia repair implant interventions. Randomization will be 1:1. Patient numbers were allocated to a study arm based on pre-established randomization tables. Randomization tables were created using ranblock.exe (Menne Biomed Software, Tübingen, Germany). Sealed envelopes were prepared with patient specific numbers and provided to the site. If a patient is withdrawn after they have been assigned a number, the envelope with the corresponding patient number will be considered non-transferable and may not be forwarded to another patient. The subject will be blinded to their treatment arm, but the surgeon will not.

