#### 6.2.1 Data to be collected intra-operatively:

- 1. Documentation of indication for surgery (i.e. incisional hernia, re-do hernia repair, etc.)
- 2. Documentation of size and location of hernia defect
- 3. Operative start and finish times
- 4. Determine if the subject has an active infection and if so, subject is withdrawn from study and is considered a "screen failure"

- 5. Determine if subject's abdomen is unable to be closed primarily and if so, subject is withdrawn from study and is considered a "screen failure"
- Operative procedure details including all research related information (detail in OR Notes)
   \*\*\*Make sure all details are documented in the OR note (i.e. sutures used and where, number of drains inserted and where, overlap, etc. when possible)
- 7. Type and dimensions of graft used
- 8. Product and serial numbers of graft used
- 9. Fixation procedures
- 10. Concomitant procedures
- 11. Photographic documentation of graft placement prior to closure, post-closure
- 12. Complications during surgery (note any and all complications including uncontrolled bleeding, subject becoming unstable, error with mesh placement, etc.) and record these events as AE/SAE's as applicable
- 13. Medications given during surgery

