## 7.2 Adverse Event Reporting

An Adverse Event (AE) is defined as any untoward medical occurrence in a subject enrolled into this study, regardless of its causal relationship to treatment. The Investigator is responsible for recording all AEs related to the surgical procedure or the device that are observed or reported by the subject during the study for the Sponsor. The collection of AE's shall begin immediately after the patient has had a porcine derived dermal matrix surgically implanted. AEs related to the surgical procedure or the device that occur from surgery through completion of the final follow-up visit, whether observed by the investigator or by the subject, shall be reported in detail on the appropriate CRFs and followed to resolution or the end of the subject's study participation.

In the event a subject reports an AE outside the scheduled clinical visit, it will be assessed at the earliest opportunity by the Investigator.

In following up AEs, attempts will be made to obtain as much information as possible about event evolution and outcome. Every effort will be made to follow the subject until resolution of the AE.

Adverse Event/Serious Adverse Evaluation

Degree of Impairment

The Investigator will evaluate the relationship of the adverse event to the degree of impairment using the following:

- Mild: The AE is transient and easily tolerated by the subject; no limitation of usual activities
- 2. Moderate: The AE causes the subject discomfort and interrupts the subject's normal activity; some limitation of usual activities
- 3. Severe: The AE is life threatening, results in permanent impairment of a body function, causes permanent damage to a body structure, or necessitates medical or surgical intervention to preclude permanent impairment of a body function or permanent damage to a body structure; inability to carry out usual activities

Relationship of AE/ SAE to Implant

The Investigator will evaluate the relationship of the AE/SAE to the use of the implanted mesh according to the following:

- Definite: The AE/SAE follows a reasonable temporal sequence from the implantation of the implant and/or is directly attributable to the use of the implant within the repair site.

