- 2. Possible: The AE/SAE follows a reasonable temporal sequence following the implantation of the implant and the possibility of the implant's involvement cannot be excluded. However, other factors related to the surgical procedure, underlying disease, concomitant treatment or medications are presumable.
- 3. Unlikely: The AE/SAE has an improbable temporal sequence from the implantation of the implant or it can be reasonably explained by other factors, including surgical procedure, underlying disease, concomitant treatment or medications.
- 4. Not Related: The AE/SAE has no temporal sequence from the implantation of the implant or it can be explained by other factors, including surgical procedure, underlying disease, concomitant treatment or medications.

For the purposes of this study, significant adverse events will be documented and reported to the study PI, Sponsor, and appropriate oversight committee at the institution per institutional protocol

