#### 7.3 Serious Adverse Events

An Adverse Event is serious if:

- It results in death
- It is life threatening (the subject is at immediate risk of dying from the adverse experience)
- It requires inpatient hospitalization or prolongs existing hospitalization
- It results in persistent or significant disability/incapacity
- Important medical events that may not result in death, be life-threatening, or require
  hospitalization may be considered a serious adverse device effect when, based upon
  appropriate medical judgment, they may jeopardize the subject and may require medical
  or surgical intervention to prevent one of the outcomes listed in this definition

SAEs will be recorded in the CRF if they occurred as follows:

After a subject received treatment and throughout the subject's follow-up period. After the subject's follow-up period, and for which a causal relationship to treatment with either randomization group cannot be ruled out. Follow-up period is defined as the protocol-stipulated period or, for subjects prematurely withdrawn from a study, the duration of subject's participation.

Study staff are instructed to report all SAEs to the PI and Sponsor within 24 hours of becoming aware of the SAE. All follow-up SAE reports are to be completed and provided within 7 calendar days to the Sponsor, allowing time for more complete reports.

All Serious Adverse Events (SAEs) must be reported to:

Clinical Projects RTI Surgical, Inc. [name] (P) [contact] (F) [contact] and RTI Customer Service [contact] [contact]

In addition to documenting SAEs on the Case Report Forms, a separate SAE form must also be completed. SAEs must also be reported either by telephone, email or by FAX by the Investigator, study coordinator, or other designated study personnel, or clinical research associate within twenty-four (24) hours of becoming aware of the SAE. Follow up information must be reported as it becomes available, this may include records such as subject X-Rays, Admission and Discharge summaries, etc.

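### Section 7.1 records an adverse event, even a serious one, only if it is judged related; this contradicts 7.3 and lets apparently unblinded attribution decide which events enter the safety data

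*Combined protocol and SAP*

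**What the plan says.** - **Recording rule, 7.1.** The first sentence says that "only adverse events or serious adverse events that are related to the surgical procedure or device will be recorded". The next sentence narrows the safety assessment to device-related AEs and leaves out those related only to the procedure.
- **Definition and duty, 7.2.** An AE is any untoward occurrence, "regardless of its causal relationship to treatment". The Investigator, however, is to record those related to the procedure or device. The Investigator also grades relationship on a four-level scale that refers to the implant only; its last level begins "Not Related: The AE/SAE has no temporal sequence from the implantation of the implant".
- **SAEs, 7.3.** SAEs go into the CRF from treatment through follow-up with no relatedness condition. Causality matters only for SAEs arising after follow-up. In addition, "Study staff are instructed to report all SAEs to the PI and Sponsor within 24 hours of becoming aware of the SAE".
- **Endpoints, 2.4.3.** The safety endpoints are AE type and "Frequency of Adverse Events (volunteered and elicited"), without restriction to related events.
- **Blinding, 5.3.2.** "The subject will be blinded to their treatment arm, but the surgeon will not". Section II gives the blinded independent evaluator one task, confirming recurrence.
- **Start of collection.** 7.2 says "The collection of AE's shall begin immediately after the patient has had a porcine derived dermal matrix surgically implanted", but later in the same section counts related AEs from surgery onward. Item 12 of 6.2.1 covers complications during the operation and asks staff to "record these events as AE/SAE's as applicable".

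**The concern.** When relatedness is a condition of entry, an event judged unrelated leaves no record. It cannot be re-graded, counted in a sensitivity table or noticed later as part of a pattern. The expected recorded frequency in an arm is then the true frequency multiplied by the chance that the recorder calls an event related. If that chance differs between arms because the recorder knows the implant, the recorded frequencies can differ when the true ones do not, or agree when the true ones differ. This trial compares the sponsor's product with a competitor's, and section 3.4 has the data summarised for regulators about every 12 months.

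The contradictions matter without any assumption about bias. Two coordinators who follow different sections would produce different safety datasets from the same patients.

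**Working it through.** The plan states no AE rate or attribution rate, so there is no figure to reproduce. The first three steps set the sections side by side, and the last is an illustration.

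**1. The safety sections compared**

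| Question | One place | Another place |
|---|---|---|
| Is an SAE judged unrelated, during follow-up, recorded? | 7.1: no | 7.3: yes, and reported within 24 hours |
| Is an AE related to the procedure but not the device in scope? | 7.1 first sentence, 7.2: yes | 7.1 second sentence: no |
| Is AE frequency limited to related events? | 7.1, 7.2: yes | 2.4.3: no limit stated |
| Is a complication during surgery, before implantation, an AE? | 7.2 start rule: no | 6.2.1 item 12: yes; 7.2 also says from surgery; 6.10 marks AEs at the surgery visit |

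Section 7.3 cannot be read as silently inheriting the 7.1 filter. It has its own causality condition, attached only to SAEs after follow-up, and that condition would be redundant if relatedness were always required.

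**2. Who applies the filter.** Under 7.2 it is the Investigator. Section 2.2 describes the Investigator as performing the repair, and 5.3.2 leaves the surgeon unblinded. No blinded AE assessment is described. That the recorder is unblinded follows by inference; no sentence says so directly.

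**3. What the filter is measured with.** Entry depends on relationship to the procedure or the device. The only graded scale, in 7.2, is for the implant. Section 7.4 mentions the relationship to the procedure for unanticipated events but gives no scale.

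**4. Illustration of size.** Inputs from the plan: 60 per arm (3.1) and Fisher's exact test for categorical outcomes (3.2). Assumptions: two-sided 5% test; a true proportion of subjects with an AE of 50% in both arms; attribution probabilities s as shown; k events per affected subject, judged independently.

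Recorded proportion = 0.50 × [1 − (1 − s)^k]. The rejection rate is the exact binomial sum over all tables with Fisher p ≤ 0.05.

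| Attribution | k | Recorded proportions | Rejection rate |
|---|---|---|---|
| 90% v 90% | 1 | 45.0% v 45.0% | 3.4% |
| 90% v 80% | 1 | 45.0% v 40.0% | 6.1% |
| 90% v 75% | 1 | 45.0% v 37.5% | 9.8% |
| 95% v 70% | 1 | 47.5% v 35.0% | 22.9% |
| 90% v 75% | 2 | 49.5% v 46.9% | 4.3% |
| 95% v 70% | 2 | 49.9% v 45.5% | 5.7% |

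For example, with k = 2 and s = 0.75, 0.50 × (1 − 0.25²) = 0.469. With k = 3 the rejection rates for the last two attribution pairs fall to 3.6% and 3.7%. Correlated judgements within a subject would fall between the k = 1 figure and the independent case.

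The result also depends on the true rate. At 90% v 80% and k = 1, the rejection rate is 4.2%, 6.1% and 8.9% for true rates of 30%, 50% and 70%.

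**The case against.** The strongest reply is that the filter does little harm in practice.

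- **The gate is broad.** Both arms have the same operation, so most wound, infectious and abdominal events can qualify as procedure-related whichever implant was used. Knowledge of the implant would mainly affect the implant grade and not entry. This stands, except under the device-only sentence of 7.1.
- **Key complications are captured elsewhere.** Fluid collection, surgical-site and systemic infection, fistula, dehiscence and implant removal are secondary endpoints in 2.4.2 with no relatedness condition, and most are elicited at every post-operative visit (6.3 to 6.8). This also stands. It leaves exposed the AEs outside that list and, if 7.1 is followed literally, SAEs.
- **The start-of-collection conflict is minor.** 7.2 and the schedule both refer to surgery, and 6.2.1 captures these complications. It is a wording repair, but still needed.
- **A limited post-market scope is legitimate.** That supports collecting fewer types of event. It does not support selecting events by a judgement that may be unblinded.

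A reader might also draw two stronger conclusions that the documents do not support. One is that the filter leaves the Unlikely and Not Related grades almost empty. Those grades concern the implant alone and name the procedure as an alternative explanation, so a procedure-related event can pass the filter and fall there. The other is that unanticipated device problems would be invisible. Section 7.4 is a separate reporting duty without a relatedness condition, and 7.2 also asks for significant adverse events to be documented and reported.

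**Conclusion.** The concern holds in limited form. The contradictions between 7.1 and 7.3 on SAEs, within 7.1 on scope, and between 7.2 and 6.2.1 on the start of collection are in the text and need no assumption. Followed literally, 7.1 drops every SAE judged unrelated.

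That entry of SAEs and unlisted AEs can depend on unblinded attribution rests on the inference that the Investigator who records events is the operating surgeon. The protocol does not exclude a blinded team member doing so.

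The size of any bias is unknown. It would be tempting to cite 9.8% or 22.9% as the false-positive rate of the safety comparison. Both require one event per affected subject and an attribution gap for which the documents give no basis; with two independently judged events they fall to 4.3% and 5.7%. Nor does the plan name a between-arm test for AEs: Fisher's test is taken from its general rule for categorical outcomes. The case for change therefore rests on the contradictions and on the loss of unrecorded events, and the arithmetic only shows that the effect could range from negligible to material.

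**What to change.** Replace the two sentences of 7.1, and the matching recording sentences of 7.2, along these lines:

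> All SAEs from surgery through the end of follow-up, and all AEs on a pre-listed set of wound, abdominal, infectious and implant-site events, are recorded in both arms regardless of judged relationship. Relationship to the implant and relationship to the procedure are recorded as two separate data fields and do not determine whether an event is entered.

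Then:

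- base the main safety table on all recorded events, with related events in a secondary table, and say whether it counts subjects or events;
- define any remaining limit on scope by type of event and not by judged relatedness;
- give one start point for AE collection in 7.2 that agrees with 6.2.1 item 12;
- check 7.1 to 7.4 and 2.4.3 against each other for consistent scope.

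The cost is a protocol amendment, one further relationship field and some extra CRF entries for unrelated events. Sample size and visits do not change. The amendment should come early, because events never entered may not be recoverable later.

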## 7.2 Adverse Event Reporting

An Adverse Event (AE) is defined as any untoward medical occurrence in a subject enrolled into this study, regardless of its causal relationship to treatment. The Investigator is responsible for recording all AEs related to the surgical procedure or the device that are observed or reported by the subject during the study for the Sponsor. The collection of AE's shall begin immediately after the patient has had a porcine derived dermal matrix surgically implanted. AEs related to the surgical procedure or the device that occur from surgery through completion of the final follow-up visit, whether observed by the investigator or by the subject, shall be reported in detail on the appropriate CRFs and followed to resolution or the end of the subject's study participation.

In the event a subject reports an AE outside the scheduled clinical visit, it will be assessed at the earliest opportunity by the Investigator.

In following up AEs, attempts will be made to obtain as much information as possible about event evolution and outcome. Every effort will be made to follow the subject until resolution of the AE.

Adverse Event/Serious Adverse Evaluation

Degree of Impairment

The Investigator will evaluate the relationship of the adverse event to the degree of impairment using the following:

- Mild: The AE is transient and easily tolerated by the subject; no limitation of usual activities
- 2. Moderate: The AE causes the subject discomfort and interrupts the subject's normal activity; some limitation of usual activities
- 3. Severe: The AE is life threatening, results in permanent impairment of a body function, causes permanent damage to a body structure, or necessitates medical or surgical intervention to preclude permanent impairment of a body function or permanent damage to a body structure; inability to carry out usual activities

Relationship of AE/ SAE to Implant

The Investigator will evaluate the relationship of the AE/SAE to the use of the implanted mesh according to the following:

- Definite: The AE/SAE follows a reasonable temporal sequence from the implantation of the implant and/or is directly attributable to the use of the implant within the repair site.
- 2. Possible: The AE/SAE follows a reasonable temporal sequence following the implantation of the implant and the possibility of the implant's involvement cannot be excluded. However, other factors related to the surgical procedure, underlying disease, concomitant treatment or medications are presumable.
- 3. Unlikely: The AE/SAE has an improbable temporal sequence from the implantation of the implant or it can be reasonably explained by other factors, including surgical procedure, underlying disease, concomitant treatment or medications.
- 4. Not Related: The AE/SAE has no temporal sequence from the implantation of the implant or it can be explained by other factors, including surgical procedure, underlying disease, concomitant treatment or medications.

For the purposes of this study, significant adverse events will be documented and reported to the study PI, Sponsor, and appropriate oversight committee at the institution per institutional protocol

